#### STATISTICAL ANALYSIS PLAN

Cohort demographics were analyzed using descriptive statistics. Continuous variables were summarized using the mean, and standard deviation (SD) or median and interquartile range (IQR) and compared using the Student t-test for normally-distributed data and the Wilcoxon rank-sum test for data with skewed distribution. Categorical variables were summarized using counts and frequency as a percentage and compared using Chi-Square test or Fisher's exact test. A p-value  $<0.05$  was considered statistically significant. Statistical analysis was performed with SAS 9 statistical software (SAS Institute, Cary, NC).

#### Power calculation

The number of subjects enrolled was based on other studies, with the assumption that up to 20% of patients in the air insufflation group would report some degree of abdominal pain after endoscopy. We estimated that the frequency of reported abdominal pain in the CO2 group would be one-fourth of that (5%) seen in the air group. To accomplish this, a minimum total of 150 subjects would be needed (significance level of 5%, power of 80%) so we aimed to recruit a total of 180 patients (enrollment ratio of 1).

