Collected data included patient demographics (age, sex, growth parameters), procedure indication, patient's overall health status based on the American Society of Anesthesiologists (ASA) classification, endoscopy-related characteristics (duration, trainee vs faculty endoscopist and complications) and anesthesia-related parameters (duration, medication dosing, and complications). Vital signs, including EtCO₂, heart rate, respiratory rate, oxygen saturation, and blood pressure were monitored and automatically recorded continuously throughout the procedure, according to the anesthesia protocol. EtCO₂ was monitored and continuously sampled by nasal prong or via capnography for intubated patients.

Outcome Measures

Patient discomfort was assessed using 3 scales:

1. Face, Legs, Activity, Cry, and Ability to be Consoled (FLACC) behavioral assessment score
2. Global Parent Perception of Pain (PPP) scale
3. FACES scale; for neurodevelopmentally appropriate children 5 years and older.

Pain

FLACC at baseline, within 15 minutes of return to recovery area, when awake. FLACC scores categorized as no pain, mild pain, moderate to severe pain, very severe pain or worst pain ever

PPP at baseline, when awake and 4 hours post discharge. PPP scores categorized as no pain, mild pain, moderate to severe pain, very severe pain or worst pain ever

VAS at baseline, when awake and 4 hours post discharge. VAS scores categorized as no pain, mild pain, moderate to severe pain, very severe pain or worst pain ever

Abdominal girth at baseline, after procedure, at discharge, and 4 hours post discharge

Endoscopist assessment

Perceived ease of inflation: easy or average, mild difficulty, very difficult

Perceived patient discomfort: comfortable or average discomfort, above average discomfort

Endoscopist guess of inflation gas

Abdominal girth was measured by the same nurse at the level of the umbilicus before the procedure, immediately upon arrival in the recovery area after the procedure, and again just before discharge. Patients were sent home with a tape measure and a postage-prepaid response card on which they recorded the abdominal girth four hours after completion of the procedure. Parents were also asked to indicate if the patient had experienced belching, bloating or flatulence.

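### The power calculation's 5% and 80% are tied to no pain scale or time in the supplied text; testing the four to six candidate assessments at unadjusted p<0.05 would put the false-positive chance at about 11–26% (chi-square) or 5–18% (Fisher)

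*SAP*

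**What the plan says.** The SAP (Power calculation) sizes the trial on the share of patients who "would report some degree of abdominal pain after endoscopy": up to 20% with air and 5% with CO2. It concludes that "a minimum total of 150 subjects would be needed (significance level of 5%, power of 80" (per cent), with a recruitment aim of 180 at 1:1. No scale, assessment time or cut-off is given there.

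The Protocol (Outcome Measures) says "Patient discomfort was assessed using 3 scales" and ranks none of them:

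- **FLACC**, described as "Face, Legs, Activity, Cry, and Ability to be Consoled (FLACC) behavioral assessment score". Schedule: "FLACC at baseline, within 15 minutes of return to recovery area, when awake". Grading: "FLACC scores categorized as no pain, mild pain, moderate to severe pain, very severe pain or worst pain ever".
- **PPP**, the parent's rating. Schedule: "PPP at baseline, when awake and 4 hours post discharge". Grading: "PPP scores categorized as no pain, mild pain, moderate to severe pain, very severe pain or worst pain ever".
- **A third scale**, called FACES in the list (limited to neurodevelopmentally appropriate children aged 5 or over) and VAS in the schedule. It has the same times and the same five grades as PPP.

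The SAP (Statistical Analysis Plan) assigns tests by type of variable: t-test or Wilcoxon for continuous data, chi-square or Fisher for categorical data. Its one significance rule is p<0.05. The supplied text contains no hierarchy, no multiplicity adjustment and no rule for choosing between chi-square and Fisher.

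**The concern.** A 5% significance level and 80% power describe one comparison chosen in advance. Each of the three scales has a category for no pain, so each post-procedure assessment could be read as the endpoint behind the 20% versus 5% calculation. If the one that crosses 0.05 may serve as the evidence for CO2, the pain claim as a whole is not held to 5% (2.5% in favour of CO2), and a reader cannot tell a confirmatory result from a selected one.

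The choice also decides who is analysed. Enrolment starts at 6 months, while FACES starts at 5 years, so a primary on FACES would leave out the younger children.

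**Working it through.** **1. The plan's own figure.** Inputs from the SAP: 20% and 5%, significance level 5% (two-sided assumed; the SAP does not say), power 80%, 1:1. The pooled normal formula per arm is

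n = [1.960·√(2·0.125·0.875) + 0.842·√(0.20·0.80 + 0.05·0.95)]² / 0.15² = 75.1, rounded up to 76.

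The total is 152 against 150 stated, and the formula's power at 75 per arm is 79.9%. The figure reproduces as a single yes/no comparison.

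**2. How many assessments could be that comparison.**

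- Six: FLACC 2 + PPP 2 + third scale 2, taking FACES and VAS as one scale.
- Five: if the FLACC wording means a single time in recovery.
- Four: if FLACC is left out because it is a behavioural score and the SAP speaks of pain that patients report.

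**3. Size of one test.** Exact, 90 per arm, same pain rate in both arms:

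| Pain rate | Chi-square | Fisher |
|---|---|---|
| 5% | 4.22% | 1.87% |
| 12.5% | 4.99% | 3.14% |
| 20% | 4.88% | 3.25% |

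**4. Chance of at least one false positive.** For K independent tests it is 1 − (1 − size)^K. With six tests, chi-square gives at most 1 − (1 − 0.0499)⁶ = 26.4% and Fisher at most 1 − (1 − 0.0325)⁶ = 18.0%. These are the upper ends below.

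The lower ends come from simulating correlated yes/no outcomes: equicorrelated latent normals cut at the pain rate, no treatment difference, 20,000 trials per setting, correlation up to 0.95. A latent 0.95 corresponds to 0.73–0.78 between the yes/no outcomes.

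| Tests | Chi-square, any | Chi-square, favouring CO2 | Fisher, any | Fisher, favouring CO2 |
|---|---|---|---|---|
| 6 | 13.5–26.4% | 6.7–14.1% | 6.6–18.0% | 3.3–9.4% |
| 5 | 12.3–22.6% | 6.2–11.9% | 5.9–15.2% | 3.1–7.9% |
| 4 | 10.7–18.5% | 5.4–9.6% | 5.2–12.4% | 2.6–6.3% |

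**5. Sensitivity.** With the third scale available in only 45 per arm (assumed, because of the FACES age limit), six tests give 16–27% (chi-square) or 6–17% (Fisher). With the five grades kept (20% any pain, two assumed splits across the grades), six chi-square tests give 14–23% and six Wilcoxon tests 14–26%.

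**6. Exact power for one comparison, 20% versus 5%.**

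| Total | Level | Chi-square | Fisher |
|---|---|---|---|
| 150 | 5% | 82.7% | 76.0% |
| 180 | 5% | 89.0% | 84.7% |
| 150 | 5%/6 | 58% | 50% |
| 180 | 5%/6 | 68% | 61% |

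The 5%/6 rows approximate Holm across six comparisons when only one truly differs.

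**The case against.** **The inflation needs a decision rule that the documents do not state.** This stands. Nothing says that all assessments will be tested as yes/no, or that one success is enough; the scores are graded in five levels. The percentages are therefore conditional. The gap beneath them is not: in the supplied text, 5% and 80% attach to no identified test.

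**The largest figures are unrealistic.** This stands too. A reader might infer that the false-positive rate is simply 26%. That needs six independent tests, whereas these are ratings of the same child's discomfort, some made at the same waking time. With four tests, Fisher, a 5% pain rate and correlation 0.95, the chance is about 5%, close to nominal.

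**Fisher may be used when counts are small.** At 5% pain and 90 per arm the expected count is 90 × 0.05 = 4.5. If Fisher were used whenever an expected count fell below 5 (an assumed rule), six tests at that rate would give about 9–15%. At 12.5–20% pain that rule changes nothing, and the SAP states no rule.

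**Part of the SAP was removed before review.** A primary endpoint could be named there, so a reader should not infer that the plan has none. But the sections that are present and would normally carry it (outcome measures, testing rules, power calculation) are silent.

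**Conclusion.** The concern holds in conditional form. In the supplied text, the single comparison that sizes the trial is linked to no scale or time; four to six assessments qualify; and the only rule is unadjusted p<0.05. The chance of at least one false positive is about 11–26% with chi-square and 5–18% with Fisher, about half of it favouring CO2. This rests on any-pain-versus-none testing, any one result counting, 90 per arm, 5–20% pain in both arms, and latent correlation 0–0.95. It is lowest with Fisher, four tests and a 5% pain rate.

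Two stronger readings are not supported. The sample size is not wrong, since it reproduces. Nor do the documents show an intention to pick the best result; they only leave it open.

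**What to change.** - **Name one primary endpoint:** any grade above no pain, on one scale usable at all enrolled ages, at one post-procedure time. Of the three scales, only FACES carries an age limit in the supplied text.
- **Name one test:** chi-square, once, two-sided 5%. State that the 5% and 80% apply to it alone, with exact power 82.7% at 150 and 89% at 180. If Fisher is preferred, restate power as 76% at 150 and 85% at 180, because 80% is then not met at the stated minimum.
- **Name the population:** as randomised, all patients with that assessment, with missing responses reported by arm. This matters most for a time 4 hours after discharge, when families have gone home.
- **Reconcile** the FACES and VAS naming.
- **Make the other pain and girth comparisons secondary:** Holm-adjusted, or estimates with 95% confidence intervals and no significance claim.
- **If data had been seen before the choice** (the documents are largely in the past tense): say so, report every pain comparison, and apply Holm across them.

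**Cost.** If the choice preceded the data, this is wording only and needs no extra patients; secondary outcomes become harder to call significant. If it did not, Holm across six with only one true difference leaves power of about 68% (chi-square) or 61% (Fisher) at 180, and 58% or 50% at 150. It is higher if several assessments truly differ: with all six, about 77–83% or 71–75% per comparison at 180.
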